**Implementation and Evaluation of a Diabetes Prevention
Clinical Pathway in Primary Care**

NCT05265312

Date: 7/11/2023

Introduction

Abstract and Background:

Prediabetes is a significant public health problem affecting 88 million U.S. adults. Evidence suggests that the vast majority of people with prediabetes are unaware that they have this condition and many are not receiving appropriate care for prediabetes, including referral to evidence-based programs like the Diabetes Prevention Programs. In our retrospective cohort study of patients with prediabetes from Johns Hopkins Health Systems, we found that the rates of prediabetes clinical care activities are low. In our qualitative studies, we found that primary care physician (PCP) barriers include low knowledge about Diabetes Prevention Programs and misperceptions of insurance coverage of these programs and inadequate clinical staff to address prediabetes. Common patient barriers to taking action to prevent diabetes include lack of motivation, time and resources.

Primary Hypothesis: We hypothesize that the clinical pathway will result in increased clinician screening and intervention and improve patient engagement in diabetes prevention. We will compare results from the intervention clinic compared to a control clinic. If successful, we plan to implement and test the effectiveness of this clinical pathway across the entire health system.

Purpose of the Study Protocol: As described above, we have conducted several studies to understand current practices in prediabetes care across the Johns Hopkins Health Systems. In our retrospective cohort study of patients with prediabetes from Johns Hopkins, we found that the rates of prediabetes clinical care activities are low. Within 12 months, 63.4% had repeat glycemic testing, yet only 10.4% had coded diagnoses of prediabetes, 1.0% were referred for nutrition services, and 5.4% were prescribed metformin. We were unable to evaluate uptake of Diabetes Prevention Programs (DPPs) since a referral order was not in place until recently. In our qualitative studies, we found that clinician barriers include low knowledge about DPPs and misperceptions of insurance coverage of these programs and inadequate clinical staff to address prediabetes. Common patient barriers to taking action to prevent diabetes include lack of motivation, time and resources.

Based on our prior research, comprehensive strategies are urgently needed to improve prediabetes care. Using these findings, we have designed and plan to implement a diabetes prevention clinical pathway which seeks to address some of these common clinician and patient barriers.

Study Objectives

Objective: Our primary objective to design and pilot test the diabetes prevention clinical pathway at a primary care clinic compared to a control primary care clinic.

Study Design

Overview: This is a non-randomized, quasi-experimental intervention study with one comparison group. Eligible patients include those on the prediabetes registry who are seen in the control and intervention clinics during the study period. Data is collected on eligible patients during the baseline (pre-implementation) period and prospectively during the 12-month implementation period.

Intervention Study Population Inclusion/Exclusion:

- Adults age 18 and older, on prediabetes registry, last A1c<6.5%
- Complete one visit (video or office visit) with PCP during intervention period

Blinding

While this study meets the NIH definition of a clinical trial, participants are not randomized or assigned at the patient level. The intervention is implemented clinic-wide and is intended to augment routine care (quality improvement). Therefore, the traditional terms of blinding in a clinical trial are not applicable.

Risks and Benefits

[figure not shown]
We believe the intervention involves minimal medical risk and is aligned with routine, evidence-based care. Participants may benefit from the intervention because of improved follow-up care (including visits, labs, and referrals) which may in turn result in a decreased risk of progression to diabetes. We aim to fill an important gap in knowledge about successful primary care clinic interventions to improve diabetes prevention. We hope to address the public health burden of diabetes by focusing on and improving the primary prevention of diabetes. We believe that the risks to subjects are low and reasonable given the anticipated benefits.

Withdrawal of Subjects

The intervention is intended to improve and augment routine care. Since it is implemented clinic-wide, patients will not have the option to opt out of the intervention. Furthermore, there is no outcome of treatment failure since we are not assigning patients to a particular treatment. They will receive treatments based on individual discussions with their doctor.

Study Procedures

This is a pre-/post-evaluation of a diabetes prevention clinical pathway that will be implemented over a 12-month period at the intervention clinic. Eligible patients include those on the prediabetes registry who are seen in the control and intervention clinics during the study period. Their first visit with the PCP will be considered V0 (initial data collection) and data will be collected retrospectively (12 months prior to V0) and prospectively at that visit and subsequent primary care visits (V1, V2, V3, etc.) during the 12-month intervention period (see Figure).

The diabetes prevention clinical pathway will focus on the following steps: 1) Screen/test-testing of eligible patients for prediabetes/diabetes, 2) Education- PCPs will be encouraged to take an online learning module and in-person group training on prediabetes management, and patients with prediabetes will receive a handout about prediabetes prior to their upcoming PCP visit, 3) Action- PCPs will use a shared decision-making guide and treatment algorithm to discuss options with patients at their visit, 4) Referral- patients may be referred to DPPs and/or medical nutrition therapy (MNT), and 5) Treat- patients will be scheduled for a follow-up visit within 3-9 months with their PCP or care team (NP) to continue addressing prediabetes.

Group 1 Intervention clinic patients

PCPs in the intervention clinic will be invited and encouraged to attend the 1-hour clinician training session at the beginning of the intervention. This is considered continuing medical education, and we may be able to provide continuing medical education credit for their attendance. The training session will include information on prediabetes treatment guidelines, use of EPIC clinical decision support tools and use of the patient handout to discuss treatment options. There will be interactive skills practice incorporated. This training session may occur on up to 2 occasions to capture all PCPs. We may also record the training session so that PCPs who could not attend can view it later asynchronously.

Patients with prediabetes (e.g., “active” on prediabetes registry) presenting for a routine visit in the intervention clinic will be identified using an EPIC workbench report run the week prior to their upcoming visit. These patients, presenting for in-person or video visits, will receive the handout as an attachment either via MyChart or via email sent from REDCap.

During the visit, the patients will be encouraged to bring the prediabetes handout to review with their PCP who can use the shared-decision making guide and treatment algorithm to discuss options with the patient. Several Epic clinical-decision support tools have been built to facilitate this discussion, including a prediabetes orders smartset (which includes the DPP referral) and prediabetes smart texts that PCPs can use to send patients information.

Patients who complete their visit will be invited via email (or MyChart if no email on file) to complete an online REDCap survey. They will first receive an email to complete the e-consent form which explains the study and the potential risk/benefits of joining the study. When the e-consent is completed, the patient will automatically receive a link to the survey. The survey is voluntary and will include up to 10 questions regarding their engagement in diabetes prevention behaviors and treatment, and satisfaction and acceptability of the intervention. The timing of the survey emails and reminders will be as follow: e-consent sent within 7 days of their visit and survey reminder 3 days after first invite. We will call patients who do not complete the e-consent form within 7 days of receipt and call patients who do not complete the survey within 5 days of receipt of the survey reminder. During the calls, we may offer to fill out the survey questions with the patient since our survey response rate has been low and this may increase uptake. Patients will be offered a \$10 gift card if they complete the survey. Regardless of whether patients fill out the survey, we will collect their medical record data using the PMAP database.

At the end of the visit, the patient will be encouraged to schedule a 3-6 month visit with their PCP or care team member to continue addressing prediabetes. At this follow-up visit, the same diabetes prevention clinical pathway steps will apply (i.e., handout sent before visit, survey to be completed after visit). The PCP or care team member will use the same shared-decision making guide and treatment algorithm to continue discussing treatment options with the patient.

Group 2 Control clinic patients

Patients with prediabetes (e.g., “active” on prediabetes registry) who present for a routine visit in the control clinic will be identified using an Epic workbench report. Their PCP will address prediabetes as they usually do (i.e. usual care). They can refer patients to the same interventions (DPP, MNT) or start metformin. PCPs will have access to the same Epic clinical-decision support tools as the intervention clinic does but not the shared-decision making guide and treatment algorithm to facilitate discussion. Patients will not receive the prediabetes handout.

Patients who complete their visit will be invited via email to complete an online REDCAP survey. They will first receive an email to complete the e-consent form which explains the study and the potential risk/benefits of joining the study. When the e-consent is completed, the patient will automatically receive a link to the survey. The survey is voluntary and will include up to 10 questions regarding their engagement in diabetes prevention behaviors and treatment, and satisfaction with prediabetes care. The timing of the survey emails and reminders will be as follow: e-consent sent within 7 days of their visit and survey reminder 3 days after first invite. We will call patients who do not complete the e-consent form within 7 days of receipt and call patients who do not complete the survey within 5 days of receipt of the survey reminder. During the calls, we may offer to fill out the survey questions with the patient since our survey response rate has been low and this may increase uptake. Patients will be offered a \$10 gift card if they complete the survey. Regardless of whether patients fill out the survey, we will collect their medical record data using the PMAP database.

Group 3 Intervention clinic PCPs

PCPs in the intervention clinic will be recruited to provide feedback using an online REDCap survey through an in-depth survey sent via email at 0m, 6m and 12m to gather feedback on intervention components and acceptability/satisfaction with the intervention. PCPs will receive an email from REDCap with the e-consent form. Once that is completed, the PCP will receive the survey link. All survey participants will receive a \$25 gift card for completion of the in-depth survey.

Safety and Adverse Events

Enrolled participants will be monitored throughout the study for untoward incidents (e.g., “Adverse Events”) occurring during the study. The Principal Investigator (and other designated individuals, if necessary) will conduct regular monitoring for safety concerns and provide general oversight for human subject safety requirements. Where necessary these occurrences will be evaluated for severity, attribution, and possible trends. All adverse events that are anticipated or described in the informed consent form will be logged appropriately and reported to the IRB on at least an annual basis (e.g., at continuing review).

Any Unanticipated Problems or unexpected “Serious Adverse Events” *related* to the study intervention or affecting the risk/benefit profile of the study, will be reported to the IRB promptly, and, in all cases, within 10 business days of discovery. Unplanned and non-emergent deviations from the IRB approved protocol will be logged and reported to the IRB annually at continuing review; all planned deviations will be submitted as a Change in Research to the IRB for approval and prior to implementation. All other event reporting requirements will be followed and all necessary parties will be notified of events/problems encountered in the study and/or changes in research, in accordance with all applicable regulations and guidelines.

Statistical Plan

Sample Size Determination and Power

We estimate that 1200 patients with prediabetes will be seen over the 12-month intervention period within each clinic (total sample of 2400 patients). Based on this sample, we estimate we will have 100% power to detect a change in rate of referral to DPPs from 0% to 25%. Additionally, we estimate that we will have 100% power to detect a change in documented prediabetes diagnosis from 10% (baseline rate estimated from Johns Hopkins data) to 34% (national estimate of the prevalence of prediabetes), follow-up lab testing completed from 50% (baseline rate estimated from Johns Hopkins data) to 60%, and referral to nutrition from 1% (baseline rate estimated from Johns Hopkins data) to 10%. In our analysis, we will assess the differences in trend of the outcomes in the baseline, intensive implementation, and sustainment periods.

Primary outcome variable

The primary outcome is whether patients with prediabetes are referred to a DPP and/or medical nutrition therapy and/or start metformin.

Secondary outcome variables

The secondary outcomes are whether patients: 1) enroll in the DPP, 2) attend a medical nutrition therapy visit, 3) complete follow-up glycemic testing, 4) fill metformin, 5) achieve weight loss $\geq 5\%$ and 6) complete PCP/team follow-up visit.

Other process outcomes we will look at include whether MyChart messages with the prediabetes handout are read.

Statistical Methods

For the analysis, we will include patients with prediabetes (identified by prediabetes registry) who have completed at least once PCP visit during the first 6 months of the 12-month intervention period. We will compare the primary outcomes and other secondary outcomes between the intervention and control clinics.

We will conduct an interrupted time series analysis to evaluate the differences in trend of the outcomes in the baseline (V0-12m), intensive implementation (T0-T6m), and sustainment periods (T6m-T12m) at the patient level. We will compare these outcomes in the pre- and post-intervention periods using logistic regression models with generalized estimating equations to account for repeated observations within patients. We will use multivariate logistic regression models to determine predictors of these outcomes adjusting for race, age, and baseline HbA1c. We may adjust for clinic-level characteristics, such as patient safety culture using GLINT survey data from 2021 and 2022 if available. We will only request aggregate data from the clinic-level on safety culture.

Study Administration

Funding Source

Funding for this study is provided by the National Institute of Diabetes and Digestive Kidney Diseases under Award Number K23DK118205 (PI: [name]).

Subject Stipends and Payments

Patients who complete the survey will receive a \$10 gift card, either mailed to their home address or sent as an e-gift card based on patient preference. The last survey question will ask them to provide this information, which will not be linked to other responses. Clinicians who

complete the survey will get a \$25 e-gift card sent to the email address they provide. Again, their response to this question will not be linked to other responses.

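### Baseline runs up to V0, but intervention patients get the handout before V0: tests it prompts in that gap count as baseline in one clinic only, and the baseline definitions need reconciling

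*Combined protocol and SAP*

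**What the plan says.** **Exposure.** Under Group 1 (Study Procedures), intervention patients are "identified using an EPIC workbench report run the week prior to their upcoming visit". The Education step of the pathway says "patients with prediabetes will receive a handout about prediabetes prior to their upcoming PCP visit". Under Group 2, control patients get no handout, and no lead time is given for their report.

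**Baseline.** Study Procedures anchors it to each patient: "Their first visit with the PCP will be considered V0 (initial data collection) and data will be collected retrospectively (12 months prior to V0". Data are then collected "prospectively at that visit and subsequent primary care visits (V1, V2, V3, etc.) during the 12-month intervention period". Statistical Methods evaluates trends "in the baseline (V0-12m), intensive implementation (T0-T6m), and sustainment periods (T6m-T12m) at the patient level". I read V0-12m as V0 minus 12 months, in line with Study Procedures. T0 is not defined. The Study Design overview describes baseline differently: "Data is collected on eligible patients during the baseline (pre-implementation) period and prospectively during the 12-month implementation period".

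**Entry.** The inclusion criteria require patients to "Complete one visit (video or office visit) with PCP during intervention period". Statistical Methods narrows the analysis to those with a completed PCP visit in the first six months.

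**The concern.** The handout is the first part of the pathway to reach a patient, and it arrives before V0. If baseline runs up to V0, the days between handout and visit are exposed time labelled as pre-intervention. A patient prompted by the handout to have a glycemic test before the visit adds an event to baseline, and may lose one from follow-up. Control patients have no such exposed days, so subtracting the control clinic's change does not remove the error.

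The entry rule raises a second, separate issue. Completing a visit comes after the handout in the intervention clinic, with no handout before it in the control clinic. If the handout changes who attends, the two cohorts are selected differently. No text follows patients who were listed and sent the handout but completed no visit.

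**Working it through.** **1. The plan's own figure.** Sample Size Determination and Power gives follow-up testing of 50% rising to 60%, 1200 patients per clinic and 100% power. Alpha is not stated; I take 0.05 two-sided.

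- Standard error under no difference: √(2 × 0.55 × 0.45 / 1200) = 0.0203.
- Standard error under the target: √((0.50 × 0.50 + 0.60 × 0.40) / 1200) = 0.0202.
- z = (0.10 − 1.96 × 0.0203) / 0.0202 = 2.98, so power is 99.86%.

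The figure is reproduced and is not in dispute. The question is whether the 10-point contrast would be measured without loss.

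**2. The exposed stretch.** With about a week between report and visit, it is 7/365 = 1.9% of baseline. It can be longer: a patient who gets the handout, misses that visit and attends a later one has all the intervening days counted as baseline.

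**3. Which outcomes can be misplaced.** Study Procedures places the decision guide and treatment algorithm at the visit, and collects visit data prospectively. Referrals and metformin starts (the primary outcome) therefore fall mostly at or after V0. A glycemic test can be done before the visit, which makes follow-up testing the most exposed outcome.

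**4. Loss in the testing contrast.** Let x% of patients be tested between handout and V0 because of the handout. Testing is a yes/no outcome, so a misplaced test matters only for a patient with no other test in the period concerned. Assume that having another test is independent of being prompted, and take the plan's 50% and 60% as the chances of another test.

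- Rise in baseline: x × (1 − 0.50) = 0.5x.
- Fall in follow-up, if the test is removed from it: x × (1 − 0.60) = 0.4x.

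| Reading of the periods | Loss | x = 2 | x = 5 |
|---|---|---|---|
| Baseline is calendar time before implementation | 0 | 0 | 0 |
| Baseline runs to V0; T0 is the start of implementation (test counted in both periods) | 0.5x | 1.0 | 2.5 |
| Baseline runs to V0; T0 is V0 (test moved to baseline) | 0.5x + 0.4x = 0.9x | 1.8 | 4.5 |

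Where baseline runs to V0, the 10-point contrast becomes 9.0 at best (10 − 1.0) and 5.5 at worst (10 − 4.5). If the Introduction's 63.4% repeat-testing rate replaces 50%, the baseline rise is x × (1 − 0.634) = 0.366x, or 0.7 to 1.8 points. The documents give no value for x.

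**5. Selection on attendance.** These are illustrations with assumed inputs and no true effect. Half the patients are receptive, with action rates of 70% (receptive) and 30% (others). Without the handout, 80% of both groups complete a visit, so the cohort rate is 50%.

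- Completion 90% receptive, 80% others: (0.5 × 0.9 × 0.7 + 0.5 × 0.8 × 0.3) / (0.5 × 0.9 + 0.5 × 0.8) = 0.435/0.85 = 51.2%, a false difference of +1.2 points.
- Completion 90% and 70%: 0.420/0.80 = 52.5%, or +2.5.
- Completion 70% and 80%: 0.365/0.75 = 48.7%, or −1.3.

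The sign depends on who responds to the handout, and the documents do not settle that.

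**The case against.** The strongest reply is that the text does not settle the baseline. If the pre-implementation wording in Study Design governs, handouts sent during implementation cannot fall in baseline and the leak vanishes. The figure cited in Study Procedures is not available to me and may show the time axis. This stands as a limit on the point, but Study Procedures and Statistical Methods would then contradict Study Design, and T0 would still lack a definition.

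A reader might infer that pathway-driven referrals and metformin starts are booked as baseline, so that the primary outcome is compromised. The documents do not support that. Those actions belong to the visit, visit data are prospective, and no pre-visit ordering step is described.

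A reader might also reckon the loss at x to 2x points, which is 2 to 10 for x = 2 to 5 and could erase the testing target. For a yes/no outcome, 2x requires that none of the prompted patients has any other test in either period. The plan's rates of 50% and 60% make that implausible. Dependence between prompted and other tests could still move the loss above or below 0.5x to 0.9x.

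On selection, listed patients already have a visit booked, and a missed visit that is rebooked within six months still qualifies. The pre/post comparison within patients also removes part of any stable difference. This reduces the concern, but does not show that attendance is unaffected.

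**Conclusion.** The point holds in a limited form. As Study Procedures and Statistical Methods are written, events between handout and V0, mainly glycemic tests, count as baseline in the intervention clinic only. This biases the pre/post contrast modestly toward no effect, so it cannot produce a false benefit. The loss on the testing outcome is about 0.5x to 0.9x points, or 1.0 to 4.5 of the planned 10 for x = 2 to 5. That range rests on an assumed x, on independence, and on baseline running to V0. The primary outcome is largely unaffected.

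The conflict among Study Design, Study Procedures and Statistical Methods over baseline, with T0 undefined, needs correcting under any reading. Entry after exposure in one clinic is a structural weakness whose size and direction are unknown. A claim that it favours the intervention would go beyond the documents.

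**What to change.** Reconcile the three sections, define T0, and set one index date for both clinics that precedes exposure:

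- If baseline is anchored to the patient, use the date of the workbench report that first lists the patient's visit, and run the control report with the same one-week lead. This also covers rescheduled visits. A fixed V0 minus 7 days is less safe, because the week before may mean the preceding calendar week.
- If baseline is calendar time, use the start of implementation, set no later than the first handout dispatch.

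End baseline the day before the index date and count outcomes from that date. Report visit completion among listed patients by clinic. If approvals allow, add a sensitivity analysis of all listed patients, whether or not they completed a visit.

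The main change costs SAP wording and a date shift in the record extract, with no new patient contact. Its downside is that routine pre-visit tests move into follow-up in both clinics. The sensitivity set extends beyond the current inclusion criteria, so it may need IRB approval, and its rates are likely to be lower because it includes non-attenders.

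### Both clinics have the Epic referral tools, so the clinic contrast measures what is added to them, and the pre/post model states no clinic-by-period term to remove a shared rise in DPP referral

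*Combined protocol and SAP*

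**What the plan says.** **Hypothesis.** The Primary Hypothesis reads "We hypothesize that the clinical pathway will result in increased clinician screening and intervention and improve patient engagement in diabetes prevention". The same paragraph plans a comparison with a control clinic and, if successful, implementation and testing across the health system.

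**Intervention clinic.** Study Procedures lists five steps: screening, education, action, referral and follow-up. The Epic tools are not named among them. The Group 1 section does include their use in the clinician training, and it describes them as built to support the visit discussion, "including a prediabetes orders smartset (which includes the DPP referral) and prediabetes smart texts that PCPs can use to send patients information".

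**Control clinic.** The Group 2 section describes usual care, but "PCPs will have access to the same Epic clinical-decision support tools as the intervention clinic does". The decision guide and the algorithm are withheld from control clinicians, and for patients the section says: "Patients will not receive the prediabetes handout". Control clinicians may refer to DPP and nutrition therapy or start metformin. Training and the encouraged follow-up visit are described only for the intervention clinic.

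**Timing.** Purpose of the Study Protocol says DPP uptake could not be evaluated because "a referral order was not in place until recently". It gives no date and names no clinic. The baseline is the 12 months before each patient's first visit (V0).

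**Analysis.** The primary outcome is a composite of DPP referral, nutrition referral and metformin start. Statistical Methods plans a between-clinic comparison, an interrupted time series over three periods, and a pre/post logistic GEE. It states no clinic-by-period term and no marker for the order's go-live. The power section claims "100% power to detect a change in rate of referral to DPPs from 0% to 25" per cent.

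**The concern.** The shared tools act directly on the primary outcome, because an order set containing the DPP referral is a route to the event being counted. Two misreadings follow.

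First, a small between-clinic difference could be taken as failure of the pathway when the tools had raised referral in both clinics. A large one could be taken as the effect of everything the pathway uses, tools included.

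Second, a within-clinic rise in DPP referral could be reported as the pathway's effect when part of it came from a referral order newly available to both clinics. The conclusion feeds a decision about system-wide implementation, so it matters which components the estimate belongs to.

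**Working it through.** **1. The plan's own figure.** Inputs from Sample Size Determination and Power: 1200 patients per clinic, DPP referral 0% versus 25%. Alpha is not stated; I assume two-sided 0.05 and independent patients.

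Power = Φ[(Δ − 1.96 × SE0) / SE1], with SE0 pooled and SE1 unpooled.

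- SE0 = √(2 × 0.125 × 0.875 / 1200) = 0.0135
- SE1 = √(0.25 × 0.75 / 1200) = 0.0125
- (0.25 − 1.96 × 0.0135) / 0.0125 = 17.9, so power is 100% to rounding.

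The stated power reproduces. The point does not rest on a numerical error.

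**2. What differs between the clinics.**

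| Component | Intervention | Control |
|---|---|---|
| Order set with DPP referral, smart texts | yes | yes |
| Clinician training, including use of the tools | yes | not described |
| Patient handout | yes | no |
| Decision guide and treatment algorithm | yes | no |
| Encouraged follow-up visit | yes | not described |

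The contrast therefore estimates the last four rows, given the first. Extra tool use that training produces belongs to that effect.

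**3. What each contrast measures for DPP referral.** Suppose the order or tools alone move referral from 0% to s in both clinics, and the intervention clinic reaches 25%. The documents give no value for s, so it is varied. The pre/post change in the intervention clinic is 25 − 0 = 25 points whatever s is. The between-clinic difference is 25 − s. The difference in pre/post change is (25 − 0) − (s − 0) = 25 − s.

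| s (assumed) | Pre/post change | Between-clinic, or difference in change | Power, 1200 per clinic |
|---|---|---|---|
| 5% | 25 | 20 | 1.000 |
| 10% | 25 | 15 | 1.000 |
| 15% | 25 | 10 | 1.000 |
| 20% | 25 | 5 | 0.835 |

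Power here is for the simple between-clinic comparison of 25% with s.

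**4. When the pre/post problem arises.** If the order and order set went live before every patient's baseline window, no arrival effect falls inside the data. If either went live during the baseline, the baseline mixes time with and without it. If it went live close to the start of implementation, its effect coincides with the pre/post contrast. The documents do not say which case applies.

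**5. Precision cost of the controlled contrast.** On the risk-difference scale, with 0% baseline in both clinics and s = 10%, the standard error of the pre/post change is √(0.1875 / 1200) = 1.25 points. For the difference in change it is √((0.1875 + 0.09) / 1200) = 1.52 points.

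**The case against.** The strongest reply is that sharing the tools is a legitimate and disclosed choice of comparator. The five listed steps do not name the Epic tools, the Group 2 section states openly what is shared and what is withheld, and only intervention clinicians are trained to use the tools. Holding access equal isolates the added package, which is most of the pathway as listed. This stands. A reader might infer that the between-clinic contrast says nothing about the pathway; the documents do not support that. What remains is that the hypothesis and roll-out statement never say the effect is over and above shared tools.

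The second reply is that the pre/post mixing is inferred. The order has no date, its arrival in both clinics is deduced from shared access, and the order and the order set may have gone live at different times. A concurrent control clinic is also the usual protection against a shared change. This stands too, and it limits the point to a gap in the stated model: data from both clinics in both periods are planned, but no term uses them together.

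Three further inferences should be resisted:

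- **That the 0% is a measured rate from before the order existed.** The power section gives no source for it, unlike the 10%, 50% and 1% beside it.
- **That 20–40% of the planned effect is misattributed** (5/25 and 10/25). This depends on an assumed 5–10%, arises only if an uncontrolled pre/post change is read as the effect of the non-shared components, and covers one part of a composite. The earlier cohort already recorded nutrition referral (1.0%) and metformin prescribing (5.4%).
- **That smart texts breach the withholding of the handout.** Nothing says the smart texts contain it.

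**Conclusion.** The point holds in two parts of different strength. It is settled by the text that the between-clinic contrast estimates the added effect of training, handout, decision guide, algorithm and encouraged follow-up over shared Epic tools, and not a package that includes those tools. It is a risk, not a demonstrated bias, that the pre/post GEE credits the pathway with a rise common to both clinics. That requires the order or order set to have gone live during or after the 12-month baseline and to have raised referral in both clinics.

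The size cannot be fixed from the documents. For DPP referral it equals s, the rate that shared tools alone would produce: 5 to 10 of 25 points under the illustrative assumption. The effect on the composite cannot be derived. A reader might infer that the study is underpowered; at 1200 per clinic, power for DPP referral stays near 100% for control rates up to 15% and falls to 0.835 only at 20%. The issue is attribution.

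**What to change.** 1. **Introduction and Study Objectives.** State the between-clinic question, and the roll-out conclusion drawn from it, as the added effect of the non-shared components over Epic tools available in both clinics.
2. **Statistical Methods.** Make the pathway effect the clinic-by-period interaction, that is, the difference between clinics in pre/post change, in both the GEE and the interrupted time series. Give it on the risk-difference scale for DPP referral, because a log-odds interaction is not estimable if baseline referral is exactly 0%.
3. **Go-live dates.** Take the dates of the DPP order and the order set from Epic and enter them as a common time marker where they can be separated from the start of implementation. If they cannot, say so and rely on the interaction, which removes the shared change only if it was equal in the two clinics.
4. **Interpretation.** Keep the within-clinic pre/post change as description, and do not interpret it alone as a pathway effect.
5. **Reporting.** Show the composite's components separately, and order-set use by clinic.

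The power statement need not be reworked for this point. The cost is some rewording, one model term, the go-live dates and descriptive tables from Epic data, with no change to care or sample size. The claim becomes narrower and the estimate somewhat less precise than a simple pre/post change (1.52 against 1.25 points in the example above). With one clinic per arm, other differences between the clinics stay confounded with the intervention, and this fix does not remove them.
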